9 ELIGIBILITY

9.1 Inclusion Criteria

Participants must meet all of the following inclusion criteria to be eligible to enrol in this trial.

- 1. Able to give informed consent and willing to follow trial protocol
- 2. Aged over 18
- Patients with cancers of the right and sigmoid colon amenable to laparoscopic resection incorporating D3 lymphadenectomy, as agreed by MDT discussion following histopathological diagnosis and radiological staging.
- 4. Patients with distant metastatic disease will be eligible, provided laparoscopic resection of the cancer is part of routine clinical care.

- 5. Fit for standard laparoscopic resection
- 6. American Society of Anesthesiologists (ASA) classification ≤ 3
- Normal hepatic and renal function on most recent blood tests (to be within 30 days prior to surgery). For the purposes of the trial a normal hepatic renal function can be defined as:
 - i. Total bilirubin within normal institutional limits
 - ii. AST/ALT < 2.5 X institutional upper limit of normal
 - iii. GFR ≥ 60 mls/min/1.73m2 or Creatinine within 10% of upper value for normal institutional limits

9.2 Exclusion Criteria

Participants meeting any of the following exclusion criteria are not eligible to enrol in this trial.

- 1. Patients with cancers of the transverse and left colon (due to difficulty in defining D3 lymphadenectomy in these anatomical locations)
- 2. Past history of hypersensitivity reactions to 5-ALA or colorimetric dye.
- 3. Acute or chronic porphyria or a family history
- 4. Patients with synchronous colonic or rectal cancer (but not benign polyps)
- 5. Patients with co-existent inflammatory bowel disease, such as Crohn's disease, ulcerative colitis or active diverticulitis, which may influence the lymphatic uptake of 5-ALA
- 6. Pregnant (positive pregnancy test) or breast feeding. 5-ALA has unknown teratogenic and abortifacient effects.

In women of childbearing potential (defined as any female who has experienced menarche and who is not postmenopausal or permanently

sterilised e.g. tubal occlusion, hysterectomy, bilateral salpingectomy). a pregnancy test will be performed and evidence of a negative result will be required prior to entry into the study. In females of child bearing potential, or those patients with partners of child bearing potential trial investigators will advise on appropriate contraception (e.g. barrier method) from the point of registration to 30 days postop.

- 7. Received an investigational medicinal product at any dose within 28 days before registration
- 8. Poorly controlled or serious medical or psychiatric illness that, in the Investigator's opinion, is likely to interfere with participation and/or compliance in this clinical trial.

Where possible, the study population will be enriched with locally advanced colon cancers (CT findings of a T4 tumour, T3 tumours with an extramural depth of >5mm, as per FOxTROT definition) to obtain as much information as possible on 5-ALA for lymph node metastases.

Concerns regarding a patient's eligibility can be discussed with the SJUH Research Fellow or Chief Investigator.

9.3 Concurrent clinical trials

Patients will be screened for inclusion in other clinical trials. Providing there is no conflict, then patients may be included in both GLiSten and other trials. A notable exception is patients recruited to FOxTROT in which preoperative chemotherapy is given. This can down-stage the disease and reduce the probability of detecting lymph node metastases.

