The Japanese Society for Cancer of the Colon and Rectum has circumvented this dilemma to some extent by recommending surgical resection based on primary tumour T-stage, with D3 lymphadenectomy recommended for T3/4 disease (11). A similar strategy was adopted in the NCRI FOxTROT study; a randomised trial investigating the use of pre-operative chemotherapy +/- anti-EGFR monoclonal antibody in high risk operable colon cancer (12). Although still not perfect, CT imaging is more accurate in determining T-stage than it is for nodal status and within the context of FOxTROT has been shown to accurately select patients for pre-operative chemotherapy (13). The accuracy, sensitivity, and specificity of CT scan in selecting patients with "bad" T3/4-stage cancers was reported to be 74% (95%CI:64–82), 78% (95%CI:65–87), 67% (95%CI:49–81) respectively (9). Although this gets around, to some extent, the problem of inaccurate pre-operative staging of local disease, there is no absolute correlation between "bad" T-stage and lymph nodal status; some 50% of T4 cancers will not have metastatic disease to the lymph nodes.

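### The restriction on preoperative chemotherapy is tied to membership of another trial, not to the treatment, so patients given it outside a trial can enter and count in the dose cohorts

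*Protocol*

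**What the plan says.** Protocol section 9.3 sets a general condition for co-enrolment: "Providing there is no conflict, then patients may be included in both GLiSten and other trials". It then singles out one trial: "A notable exception is patients recruited to FOxTROT in which preoperative chemotherapy is given". The reason follows: "This can down-stage the disease and reduce the probability of detecting lymph node metastases". This is the only restriction on preoperative chemotherapy in the protocol.

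Section 9.2 opens by stating that "Participants meeting any of the following exclusion criteria are not eligible to enrol in this trial". None of its eight numbered items mentions chemotherapy, neoadjuvant treatment or FOxTROT. The nearest is item 7: "Received an investigational medicinal product at any dose within 28 days before registration". The synopsis criteria are also silent on prior chemotherapy.

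Section 9.1, item 4, states: "Patients with distant metastatic disease will be eligible, provided laparoscopic resection of the cancer is part of routine clinical care". It sets no condition on earlier systemic treatment. Section 9.2 closes with the recruitment aim: "Where possible, the study population will be enriched with locally advanced colon cancers", defined by the FOxTROT CT criteria. Section 6.3 describes FOxTROT as "a randomised trial investigating the use of pre-operative chemotherapy" in high-risk operable colon cancer.

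Section 8.1 bases its decisions on groups of 10 node-positive patients: two initial dose cohorts, then a confirmation stage of at least 10. Section 17 defines the primary analysis population as everyone who received 5-ALA.

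**The concern.** The stated reason and the rule do not cover the same patients. The reason concerns what chemotherapy does to nodal disease. The rule concerns which other trial a patient has joined. A patient given the same treatment in routine care carries the same problem and is not covered.

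Two consequences are possible. A treated patient may be node-negative on histology, in which case another must be recruited to reach 10 positives. Or the patient may stay node-positive with partly treated nodes. If such nodes fluoresce less, a missed node would reflect the earlier treatment rather than the 5-ALA dose. The cohorts are recruited one after the other, so nothing balances treated patients between doses. Results in the first cohort determine which dose the second receives.

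**Working it through.** **Which routes are closed?** Take a patient who has had preoperative chemotherapy for the current cancer.

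| Route | Provision that applies | Closed? |
|---|---|---|
| Within FOxTROT | 9.3, named exception | Yes |
| Within another trial | 9.3, no-conflict condition; 9.2 item 7 if an investigational product was given within 28 days before registration | Arguably; conflict is not defined |
| Routine care, no trial | None in 9.1, 9.2, 9.3 or the synopsis | No |

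Item 7 does not close the third route, because routine chemotherapy is not an investigational product. The no-conflict condition does not close it either, because it concerns other trials.

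**The plan's own figures.** The two-sided exact 99% upper bound for x detected out of n is the 0.995 quantile of Beta(x + 1, n − x). With n = 10:

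- 1/10 gives 54.4% and 2/10 gives 64.8%. The smallest count whose bound reaches 60% is therefore 2, as section 8.1 states.
- 3/10 gives 73.5% and 4/10 gives 80.9%. If the confirmation stage has 10 node-positive patients, the 80% rule needs 4.

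At either boundary a single patient decides the outcome.

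**Yield (illustration).** Section 8.1 plans on 10/16 = 62.5% node-positive. Let c be the treated fraction of a cohort and r the node positivity of treated patients relative to plan. Both are assumptions that the protocol does not supply. Then p = 0.625 × (1 − c + c·r), and the expected number treated to reach 10 positives is 10/p.

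| c | r | p | 10/p | Chance of at least 10 positives in 16 |
|---|---|---|---|---|
| 0 | – | 0.625 | 16.0 | 0.61 |
| 0.1 | 0.8 | 0.625 × 0.98 = 0.6125 | 16.3 | 0.57 |
| 0.2 | 0.6 | 0.625 × 0.92 = 0.575 | 17.4 | 0.45 |
| 0.3 | 0.4 | 0.625 × 0.82 = 0.5125 | 19.5 | 0.26 |

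**Progression rules (worst case, illustration).** Suppose 3 of the 10 node-positive patients were treated and none of them could be detected. Both are assumptions.

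- 2-of-10 rule, one cohort, true sensitivity 60% in the other seven: P(at least 2 of 7) = 1 − 0.4⁷ − 7 × 0.6 × 0.4⁶ = 1 − 0.0016 − 0.0172 = 0.981. With 10 untreated patients the figure is 0.998.
- 80% rule with 10 patients, true sensitivity 80% in the other seven: P(at least 4 of 7) = 1 − (0.00001 + 0.00036 + 0.00430 + 0.02867) = 0.967. With 10 untreated patients it is 0.999.

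**Observed detection rate (same worst case).** With k undetectable patients and sensitivity s in the rest, the expected rate is s × (10 − k)/10. At s = 60% and k = 0, 1, 2, 3 it is 60%, 54%, 48% and 42%. The comparison between doses is therefore more exposed than the progression rules.

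**The case against.** Several points on the other side stand.

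- A reader might infer that the restriction lies outside the eligibility rules altogether. It does not. Section 9.3 belongs to the eligibility section, and section 13.2 has patients assessed against Section 9 as a whole. Section 10.2 also requires an eligibility checklist, whose content is not shown.
- A reader might infer that patients treated in any other trial can enter freely. The no-conflict condition comes before the FOxTROT sentence, and a trial giving preoperative chemotherapy would raise the same conflict. That route is at least partly covered.
- A reader might infer that the rule wrongly turns away FOxTROT patients allocated no preoperative chemotherapy. Section 6.3 says only that FOxTROT is randomised and investigates preoperative chemotherapy with or without an antibody. It does not describe an arm without chemotherapy, so the protocol does not support that inference.
- A reader might infer that down-staging biases the sensitivity estimate. Patients who become node-negative never enter the denominator, because recruitment continues to 10 positives. They cost yield, not validity.
- The protocol does not say that residual positive nodes fluoresce less after chemotherapy. Section 8.1 also bases the dose choice on node-level information and practical considerations, not on the detection rate alone.

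None of this reaches chemotherapy given in routine care. That gap remains, and an analysis plan cannot close it by adding an eligibility criterion.

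**Conclusion.** The concern holds in a limited form. The reason in 9.3 applies to preoperative chemotherapy in general, but the restriction works only through trial membership. Patients treated outside a trial can be enrolled and counted among the 10.

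The size is unknown. The protocol gives no number of such patients, and it may be zero. On the assumed ranges, the yield effect is between 0.3 and 3.5 extra patients per cohort (16.3 − 16 and 19.5 − 16). The effect on the dose comparison depends on an unproven loss of fluorescence in treated nodes.

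It would be tempting to say that two treated patients use up the whole 2-of-10 threshold. They do not: the rule needs two detections, not eight, and either cohort can supply them. Even with three undetectable patients, one cohort would still pass with probability 0.981 at a sensitivity of 60%. What remains is an avoidable source of mixing in small sequential cohorts, where one patient can matter at a decision boundary. It is worth correcting because the correction is cheap.

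**What to change.** Reconcile section 9.3 with sections 9.1 and 9.2 and the synopsis in one of two ways. The choice is for the sponsor and investigators.

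1. Key the restriction to preoperative chemotherapy received for the current cancer, in or out of a trial, and state it in the eligibility lists as well as in 9.3.
2. Keep such patients, for example those with metastatic disease, but record the treatment on the case report form. State that they do not count toward the 10 informative node-positive patients used for the 2-of-10 rule, the dose choice and the 80% rule.

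The cost is a short amendment: one eligibility line and one revised sentence, or one data item and one counting rule. The downside is that a few patients are lost or do not count, which may lengthen recruitment slightly.

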9.4 Surgeon eligibility

The two surgeons participating in this developmental study:

- are proficient with laparoscopic colon cancer surgery.
- are able to recruit a minimum of 24 patients each over a period of 18 months.

- have appropriate and willing radiological and histopathological support.
- are familiar with the principles of Good Clinical Practice.
- have the necessary research support infrastructure

10 RECRUITMENT PROCESS

Both research sites will be required to have obtained ethical, competent authority and management approval prior to opening to recruitment.

10.1 Informed Consent and Eligibility

Patients will be identified via cancer multidisciplinary team meetings and approached in outpatient clinics for participation in the study. Patients will be approached during standard clinic visits for management of their disease and will be provided with verbal and written details about the trial. This will include detailed information about the rationale, design and personal implications of the trial.

Following information provision, patients will have as long as they need to consider participation (normally a minimum of 24 hours) and will be given the opportunity to discuss the study with their family and other healthcare professionals before they are asked whether they would be willing to take part in the study.

Provision of information regarding the trial is permitted by any member of the site research team approved to do so by the Principal Investigator, although the Principal Investigator should be informed of any patients approached to participate by any other member of the site research team.

Assenting patients will then be assessed for eligibility and invited to provide informed, written consent. The Principal Investigator or any other clinically qualified member of the trial team who has received GCP training, and who is approved by
the Principal Investigator, is permitted to take informed consent. The right of the patient to refuse consent without giving reasons will be respected. Further, the patient will be free to withdraw from the study at any time without giving reasons and without prejudicing any further treatment.

A record of the consent process detailing the date of consent and all those present will be kept in the patient notes. The original consent form will be filed in the Investigator Site File, a copy of the consent form will be given to the patient and a copy will be returned to Research Fellow at SJUH

10.1.1 Loss of capacity following informed consent

Where valid, informed consent is obtained from the patient and the patient subsequently becomes unable to give informed consent by virtue of physical or mental incapacity, the consent previously given when capable remains legally valid. Participants who lose capacity after informed consent has been obtained will continue with protocol treatment and follow-up at the discretion of the treating investigator.

11.1.2 Colorimetric dye and 5-ALA administration

As part of their normal investigation for bowel cancer, all patients undergo endoscopic examination. It is usual practice on finding a colon cancer to tattoo the lesion with India ink as a means of identifying it during laparoscopic surgery. We will standardise the method by which India ink tattooing is performed so as to be consistent between all patients recruited into GLiSten.

Participants will be admitted to hospital and undergo bowel preparation according to institutional preference. Colorimetric dye (India ink) will be administered at colonoscopy at the time of cancer investigation and diagnosis. This is routine practice for tumour localisation tattooing prior to laparoscopic colorectal surgery.

Oral 5-ALA solution will be administered at 4-6 hrs prior to operation.

11.2 Surgery: Segmental colectomy with D3 lymphadenectomy

Participants will undergo initial laparoscopic assessment to identify the overall lymphatic anatomy (colorimetric dye) and the presence of involved lymph nodes (5-ALA). Fluorescent lymph nodes will be marked with small surgical clips (e.g. Ligaclips) to facilitate subsequent pathological identification. Patients will undergo segmental colectomy with D3 lymphadenectomy. For cancers of the right colon, segmental colectomy with D3 lymphadenectomy will include central dissection at the origin of the ileocolic, right colic (when present) and middle colic vessels, with high vascular ligation and division. Specimen extraction and ileo-colic anastomosis will be as per surgeon's preference. For cancers of the sigmoid colon, segmental colectomy will include high ligation and division of the inferior mesenteric vessels proximal to the origin of the left colic vessels. Specimen extraction and colo-rectal anastomosis will be as per surgeon's preference.

11.3 Histological assessment of lymph node status

The sites of any fluorescent nodes will be marked at operation using small surgical clips. Photographs of the fresh specimen with the clips in place with a cm scale will be taken in theatre to assist the pathologists. Resection specimens will be subjected to in depth histopathology, as per the Royal College of Pathologists guidance. See appendix 3 for further details.

Additional assessment will include:

- i) specimen photography and assessment of the completeness of mesocolic resection
- ii) distance of tumour and bowel wall to vascular ligation and length of vessels
- iii) area of lymphadenectomy
- iv) level of lymphadenectomy based on vascular anatomy
- v) histological analysis and mapping of lymph nodes identified by colorimetric

dye/5-ALA for metastatic deposits.

vi) Assessment of whether it is possible to visualise the fluorescent nodes at the time of cut up to further assist localisation of at the time of microscopy by fluorescent illumination.

11.4 Postoperative care

Participants will undergo standard postoperative care, with additional monitoring for side-effects to colorimetric dye/5-ALA, including measurement of liver function tests.

As follow-up is restricted to 30-days postoperative, for the purpose of identifying adverse events, problems with loss to follow-up will be minimal.

11.5 Withdrawal criteria

In line with usual clinical care, cessation or alteration of regimens at any time will be at the discretion of attending clinicians or the participants themselves. All participants withdrawn from treatment or prescribed alternative treatment will still attend for follow-up assessments unless unwilling to do so and CRFs will continue to be completed. The PI, or delegate should make every effort to ensure that the specific wishes of any participant who wishes to withdraw consent for further involvement in the trial are defined and documented using the Withdrawal CRF in order that the correct processes are followed by the SJUH Research Fellow and site following the withdrawal of consent. It should be made clear to any participant specifically withdrawing consent for further data collection in a CTIMP that data pertaining to safety will continue to be collected for regulatory reporting purposes and will be included in any safety analysis. In addition it is suggested that the participant is made aware of the fact that if any significant new information becomes available in regard to the treatment they have received in the trial it may be necessary to contact them in the future.

All patients will be able to withdraw from the study at any time, and will be reassured that this will not influence their subsequent standard of care. Specific reasons for patient withdrawal might include:

- Concern relating to involvement in a clinical trial of an investigational product.
- Concern regarding adverse effects of 5-ALA administration.

12 Trial Medicinal Product Management

12.1 Investigational Medicinal Products

The following are classified as Investigational Medicinal Products (IMPs).

• 5-ALA

5-ALA (in the form of its hydrochloride, 5-ALA HCI) has been used in humans for fluorescence diagnosis and photodynamic therapy in a variety of cancers. It preferentially accumulates in cancer cells where it is metabolised to Protoporphyrin IX (PpIX), a component of the Heme pathway and an endogenous photosensitiser (22).

5-ALA is safe for human administration; it is used topically in dermatological malignancies, intravesically to detect bladder cancers, and orally in premalignant oesophageal lesions and malignant gliomas (23). It has also been administered intradermally, intraperitoneally and intravenously in experimental studies without adverse effects. 5-ALA is available in various forms depending on the intended mode of application. When administered orally in high doses for photodynamic therapy, side-effects may include nausea, tachycardia, hypotension, photosensitivity, and a transient rise in aspartate transaminase and bilirubin When 5-ALA is administered orally in conjunction with surgical resection of malignant brain tumours side effects can include brain oedema. 5-ALA is cleared by the liver and kidneys with a short half-life and return to baseline levels by 24 hours. Much smaller doses are required for fluorescence diagnosis; typically 20 mg/kg.

Please refer to the Pharmacy and IMP Trial Site Operating Procedure for full details of the trial IMP management requirements, including details of IMP labelling,

destruction, accountability and disposal records.

12.2 IMP supply, labelling and IMP handling

5-ALA will be supplied by photonamic GmbH & Co.KG, Germany with a trial specific label, in line with Directive 2001/20/EC and the Medicines for Human Use (Clinical Trials) Regulations 2004 (amended 2006). It must be ring fenced for this trial in a separate area to non-trial products and records retained in the Pharmacy Site File noting the location of the storage.

Please refer to the Pharmacy and IMP Management Trial Site Operating Procedure for full details of the trial IMP management requirements.

12.3 IMP Preparation

5-ALA will be prepared and handled in line with manufacturers' recommendations.

12.4 5-ALA Administration

5-ALA will be supplied in a sterile powder format to be reconstituted by dissolving in tap water immediately prior to oral administration. The dose of 5-ALA will be administered at either10 mg/kg, 20 mg/kg or 30 mg/kg.

12.5 Concomitant Medications

The only absolute contra-indications to the use of 5-ALA are

- A previous history of hypersensitivity to photosensitising drugs
- A previous history of acute or chronic porphyria
- Hepatic or renal dysfunction
- Pregnancy

5-ALA should be used with caution:

- With other medications known to have a photosensitising effect e.g. tetracylines, sulphonamides, quinolones. Patients should not be exposed to any photosensitizing agent up to 2 weeks after administration of 5 ALA
- With other medications associated with acute porphyria e.g. diclofenac, barbiturates, carbamazepine, phenytoin
- With other medication associated with hepatic or renal dysfunction e.g. NSAIDs, ACEinhibitors, loop diuretics, phenytoin

